7.2. Discontinuation of Study Intervention

In some instances, it may be necessary for a participant to permanently discontinue study intervention. Reasons for permanent discontinuation of study intervention may include the following:

- Participant did not achieve CR/CRi at the end of the reinduction treatment cycle.
- Criteria for restarting study intervention after interruption were not met.
- Treatment-related AE of unacceptable severity.
- Participant requests to discontinue study intervention.
- Investigator determines discontinuation is in the best interests of the participant for safety, behavioral, compliance, administrative, or other reasons.

Participants who discontinue study intervention early will complete the early discontinuation assessments (refer to the Schedule of Activities/Assessments; Section 1.2) and will continue to be followed-up for outcomes in the long-term follow-up period of the study until death or for 5 years after randomization.

7.3. Participant Withdrawal from the Study

- It is expected that all participants randomized in the study, regardless of completion or discontinuation of study intervention, will remain in the study for long-term follow-up.
- Before withdrawing a participant from the study, clarify and document the specific expectations of the participant's request for withdrawal. The following withdrawal scenarios may apply:
 - Discontinuation of study intervention, but completes remaining study assessments, and agrees to collection of relevant follow-up information (i.e., remains in the study; this is the default scenario).
 - Discontinuation of study intervention and/or refuses further study-specific assessments, but agrees to collection of relevant follow-up information (i.e., remains in the study).
 - Completion or discontinuation of study intervention and/or refuses further assessments, AND withdraws consent for any further study communication or

follow-up from the study center (i.e., withdraws from the study); the investigator must document this in the site study records.

- A participant may withdraw from the study at any time at his/her own request, or may be withdrawn at any time at the discretion of the investigator for safety, behavioral, compliance, or administrative reasons.
- At the time of withdrawing from the study, if possible, an early withdrawal visit will be conducted. See the Schedule of Activities/Assessments (Section 1.2) for data to be collected at the time of study withdrawal and follow-up and for any further evaluations that need to be completed.
- If the participant withdraws consent for disclosure of future information, the sponsor may retain and continue to use any data collected before such a withdrawal of consent.
- If a participant withdraws from the study, he/she may request destruction of any samples taken and not tested; the investigator must document this in the site study records.

Discontinuation of specific sites or of the study as a whole are discussed in [Appendix 1](#).

7.4. Lost to Follow-up

A participant will be considered lost to follow-up if he/she repeatedly fails to return for scheduled visits and the study center is unable to contact the participant.

The following actions must be taken if a participant fails to return to the clinic for a required study visit:

- The site must attempt to contact the participant and reschedule the missed visit as soon as possible and counsel the participant on the importance of maintaining the assigned visit schedule and ascertain whether or not the participant wishes to and/or should continue in the study.
- Before a participant is deemed lost to follow-up, the investigator or designee must make every effort to regain contact with the participant (where possible, 3 telephone calls and, if necessary, a certified letter to the participant's last known mailing address or local equivalent methods). These contact attempts should be documented in the participant's medical record.
- Should the participant continue to be unreachable, he/she will be considered to have withdrawn from the study. The sponsor may retain and continue to use any data collected.
- The site should also make every effort to verify the participant's vital status with the participant's regular/non-study physician(s).

8. STUDY ASSESSMENTS AND PROCEDURES

Planned time points for all study assessments and procedures are provided in the Schedule of Activities/Assessments (see [Table 1](#) for induction cycles and [Table 2](#) for consolidation cycles). Adherence to the study design requirements, including all specified assessments, is essential and required for study conduct. Protocol waivers or exemptions are not allowed.

Repeat or unscheduled samples may be taken for safety reasons or for technical issues with sample quality. Record results of any unscheduled assessments or visits related to study participation in the eCRF.

8.1. Screening

All screening evaluations must be completed and reviewed to confirm that potential participants meet all eligibility criteria. The investigator will maintain a screening log to record details of all participants screened and to confirm eligibility or record reasons for screening failure.

Procedures conducted as part of the participant's routine clinical management (e.g., blood counts) and obtained before signing of the ICF may be utilized for screening or baseline purposes, provided the procedures meet protocol-specified criteria and were performed within the time frame defined in the Schedule of Activities/Assessments ([Table 1](#)). Applicable results must be entered into the participant's eCRF.

The following examinations and procedures will be conducted as part of the screening process:

- Informed consent. Written documentation of completion of the informed consent process with the potential participant (and legally authorized representative if applicable).
- Demographics, medical history (including family medical history), medication history, ECOG status (see [Appendix 5](#)), physical examination, vital signs, height, and weight.
- ECG (see Section [8.3.3](#)).
- Echocardiogram or multigated acquisition (MUGA) scan to identify pre-existing cardiac dysfunction that may exclude a participant from enrollment or contraindicate use of standard 7+3 chemotherapy. Repeat testing before subsequent cycles of chemotherapy will be per institutional standard of care.
- Clinical chemistry, hematology, fibrinogen, D-dimer, and coagulation (aPTT, prothrombin time/international normalized ration [PT/INR]) tests (see Section [8.3.4](#)).
- Analysis of bone marrow aspirate/biopsy and peripheral blood screening samples (see Section [8.2.1](#)) for confirmation of diagnosis, identification of specific translocations and inversions, and determination of genetic risk categorization and study eligibility.
- Review of all eligibility criteria to determine if participant qualifies for randomization. This includes review of results of all screening assessments and a final review for any changes in medical history, concomitant medications, or ECOG status at baseline before randomization.

8.2. Efficacy Assessments

The anti-leukemic activity of dociparstat in combination with 7+3 chemotherapy will be assessed by routine laboratory tests and examination of bone marrow aspirates/biopsies. Response criteria and outcome measures are based on definitions from ELN (Döhner 2017; also see [Appendix 7](#)).

8.2.1. Bone Marrow Aspirate/Biopsy and Peripheral Blood Assessments

Bone marrow aspirate/biopsy and peripheral blood samples will be collected for the assessments specified in [Table 6](#). Tests such as cytogenetic analyses are commonly performed locally for diagnosis of AML; central molecular genetic testing and using fluorescence in situ hybridization (FISH) is performed to facilitate rapid turnaround of tests for purposes of determining eligibility and stratification. If there is a discrepancy between results from central and local laboratories, results from the central laboratory will be used for determination of eligibility and stratification.

MRD testing of screening bone marrow samples is critical to identify leukemia associated phenotypes that are to be followed at each recovery assessment. Due to the need for high quality samples that are not hemodiluted, the ELN strongly recommends that the first bone marrow aspirate draw be used for MRD assessment.

Table 6: Bone Marrow and Peripheral Blood Efficacy Assessments

Assessment	Purpose	Laboratory • Sample Type	Timing
Multiparameter (multicolor) flow cytometry (MFC) (also see Table 9)	MRD analysis	Central laboratory • Bone marrow aspirate (*first draw*)	• Screening • Time of hematologic recovery for each treatment cycle
Biobanking (also see Table 9)	Storage and future analyses	Central laboratory • Bone marrow aspirate • Whole blood	• Screening • Time of hematologic recovery for each treatment cycle
Immunological phenotyping	Expression of cell-surface and cytoplasmic markers	Central laboratory ^a • Whole blood	• Screening
Fluorescence in situ hybridization (FISH)	Identification of rearrangements including RUNX1-RUNX1T1, CBFB-MYH11, KMT2A (MLL), and MECOM (EVI1)	Central laboratory ^a • Whole blood	• Screening
Molecular genetic testing	Including mutations in FLT3, NPM1, CEBPA, RUNX1, TP53, and ASXL1	Central laboratory ^a • Whole blood	• Screening

Assessment	Purpose	Laboratory • Sample Type	Timing
Morphology (cytology)	Identification of marrow cellularity and blast percentage	Local – Enter results in eCRF • Bone marrow aspirate	• Screening • After each treatment cycle
Cytogenetic profile (cell culture and banding analyses)	Identification of specific translocations and inversions	Local – Enter results in eCRF • Bone marrow aspirate	• Screening

^a In the event the central laboratory is not able to analyze a sample or results are delayed, local laboratory results (if available) *may* be utilized for screening/eligibility.

Study center staff must enter results of all local/institutional bone marrow analyses into the eCRF. Copies of all local pathology reports are to be retained with the participant's study records and to be available for monitoring.

Instructions for collection, handling, and shipment of samples is included in the laboratory manual.

8.2.2. Response Criteria and Outcome Measures

Response criteria and outcome measures (Table 7) are based on definitions from ELN (Döhner 2017).

Table 7: Response Criteria and Outcomes Measures

Response / Outcome	Definition
Response	Complete remission with complete hematologic recovery (CR) Defined for all study participants at the end of induction therapy. Bone marrow blasts <5%, absence of circulating blasts and blasts with Auer rods, absence of extramedullary disease, ANC >1.0 x 10 ⁹ /L (1000/µL), and platelet count >100 x 10 ⁹ /L (100,000/µL). Recovery of ANC and platelet counts within 7 days before or 7 days after bone marrow biopsy showing blasts <5% may be used to assess best response.
	CR with incomplete hematologic recovery (CRI) Defined for all study participants at the end of induction therapy. All CR criteria (bone marrow blasts <5%; absence of circulating blasts and blasts with Auer rods; absence of extramedullary disease), except for residual neutropenia ($\leq 1.0 \times 10^9/L$ [1000/µL]) or residual thrombocytopenia ($\leq 100 \times 10^9/L$ [100,000/µL]). [Note: Participants with both residual neutropenia and residual thrombocytopenia are not considered to have achieved CRI.]
	CR with partial hematologic recovery (CRh) Defined for all study participants at the end of induction therapy. CR criteria (bone marrow blasts <5%; absence of circulating blasts and blasts with Auer rods; absence of extramedullary disease), with partial recovery of peripheral blood counts (ANC >0.5 x 10 ⁹ /L [500/µL] and partial recovery of platelets >50 x 10 ⁹ /L [50,000/µL], but the count recovery criteria for CR are not met).

Response / Outcome	Definition
Measurable residual disease negative (MRD _{neg})	
Defined for all study participants at the end of induction and consolidation therapy.
 
Negative (undetectable) MRD in recovery (~Day 22-42) bone marrow, as measured by MFC (0.1% detection limit).

Failure (induction failure)	Failure to achieve CR (or CR/CRi) within 42 days of the start of induction therapy (or start of reinduction therapy when applicable).
Relapse (hematologic)	
Defined through 5 years after randomization only for participants achieving CR (or CR/CRi) during induction/reinduction.
 
After achievement of CR/CRi, bone marrow blasts $\geq 5\%$, reappearance of blasts in the blood, or development of extramedullary disease.

Cumulative incidence of relapse	
Defined through 5 years after randomization only for participants achieving CR (or CR/CRi) during induction/reinduction.
 
Measured from the date of randomization to the date of relapse. Participants not known to have relapsed will be censored on the date they were last known to be alive. Participants who die without relapse will be counted as competing-risk events.

Overall survival (OS) *Primary Endpoint	
Defined for all study participants through 5 years after randomization.
 
Measured from the date of randomization to date of death from any cause.
 
Participants not known to have died at last follow-up contact will be censored on the date they were last known to be alive.

Event-free survival (EFS) following CR *Key Secondary Endpoint	
Defined for all study participants through 5 years after randomization.
 
Measured from the date of randomization to treatment failure, relapse, or death from any cause, whichever occurs first. For this endpoint, treatment failure is defined as failure to achieve CR within 42 days of the start of induction/reinduction. Participants not known to have relapsed or died will be censored on the date they were last known to be alive.

EFS following CRi	
Defined for all study participants through 5 years after randomization.
 
Measured from the date of randomization to treatment failure, relapse, or death from any cause, whichever occurs first. For this endpoint, treatment failure is defined as failure to achieve CRi within 42 days of the start of induction/reinduction. Participants not known to have relapsed or died will be censored on the date they were last known to be alive.

Relapse-free survival (RFS)	
Defined through 5 years after randomization only for participants achieving CR (or CR/CRi) during induction/reinduction.
 
Measured from the date of randomization to date of relapse or death from any cause. Participants not known to have relapsed or died at last follow-up contact will be censored on the date they were last known to be alive.

Time to recovery of neutrophil count	
Defined for all study participants.
 
Measured as time from date of randomization until the first day the ANC is $>500/\mu\text{L}$ and is $>1000/\mu\text{L}$ following induction or reinduction (if indicated).

Response / Outcome	Definition
Time to transfusion-independent platelet recovery	
Defined for all study participants.
 
Measured as time from date of randomization until the first day the platelet count recovers to $>20,000/\mu\text{L}$, $>50,000/\mu\text{L}$, and $>100,000/\mu\text{L}$, without a platelet transfusion in the preceding 5 days following induction or reinduction (if indicated).

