3. OBJECTIVES AND ENDPOINTS

For definitions and response and outcomes criteria, refer to Section 8.2.2 and [Appendix 7](#).

Objectives	Endpoints
Primary Efficacy	

 To compare the efficacy of dociparstat plus standard chemotherapy versus standard chemotherapy alone as upfront treatment for newly-diagnosed AML 	
 Overall survival (OS).
Key Secondary Efficacy	

 To compare the efficacy of dociparstat plus chemotherapy versus chemotherapy alone with respect to event-free survival (EFS). 	
 EFS following CR. Defined as time from randomization to treatment failure, relapse, or death from any cause, whichever occurs first, with treatment failure defined as failure to achieve CR within 42 days of the start of induction (or start of reinduction, when applicable).
Secondary Efficacy	

 To compare the efficacy of dociparstat plus chemotherapy versus chemotherapy alone with respect to event- and relapse-free survival. 	
 EFS following CR/CRI, with treatment failure defined as failure to achieve CR/CRI within 42 days of the start of induction (or start of reinduction, when applicable). Relapse-free survival (RFS) after CR. RFS after CR/CRI.

 To compare MRD status with dociparstat plus chemotherapy versus chemotherapy alone. 	
 Proportion of participants who achieve CR with MRD_{neg}, as determined by multiparameter (multicolor) flow cytometry (MFC), at the end of induction and consolidation therapy. Proportion of participants who achieve CR/CRI with MRD_{neg}, as determined by MFC, at the end of induction and consolidation therapy. Proportion of participants who achieve MRD_{neg} (regardless of CR), as determined by MFC, at the end of induction and consolidation therapy. Association between CR with MRD_{neg} and relapse. Association between MRD_{neg} and relapse. Association between MRD_{neg} and OS.

 To compare post-induction response rates after treatment with dociparstat plus chemotherapy versus chemotherapy alone. 	
 Proportion of participants who achieve CR. Proportion of participants who achieve CR/CRI. Proportion of participants who achieve CR or complete remission with partial hematologic recovery (CRh).

Objectives	Endpoints

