Reinduction cycle (as indicated) – participants ≥60 years	
When reinduction is indicated, participants ≥60 years will receive a modified dosing schedule:
 
 • Cytarabine 100 mg/m²/day via continuous IV infusion for 5 days AND • Anthracycline on Day 1 and Day 2: 
 ◦ Idarubicin 12 mg/m² by slow (10 to 15 minutes) IV injection OR ◦ Daunorubicin 60 mg/m² given via rapidly flowing IV infusion 
Note: FLT3-positive participants may receive cytarabine 200 mg/m²/day
	
 • Dociparstat 4 mg/kg or placebo IV bolus on Day 1, administered 30 minutes after completion of the first dose of idarubicin or daunorubicin, followed by • Dociparstat 0.25 mg/kg/hr or placebo by continuous IV infusion for 24 hours daily for 5 days (starting on Day 1 and ending on Day 6 [120 hours])
Consolidation cycles (up to 4 cycles, as applicable)	
Only participants with a documented response (CR or CRi) are eligible for consolidation.
 
 • Cytarabine via IV infusion over 3 hours, administered twice daily (at 12-hour intervals) on Day 1, Day 3, and Day 5 
 ◦ Age 18-59 years: 3 g/m²/dose ◦ Age ≥60 years: 1.5 g/m²/dose 	
 • Dociparstat 4 mg/kg or placebo IV bolus on Day 1, administered 30 minutes after completion of the first dose of cytarabine, followed by • Dociparstat 0.25 mg/kg/hr or placebo by continuous IV infusion for 24 hours daily for 5 days (starting on Day 1 and ending on Day 6 [120 hours])

Note: Participants with a FLT3 mutation may also receive treatment with midostaurin at the investigator's discretion and dependent on local availability.

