9.4.2. Key Secondary Endpoint

The key secondary EFS endpoint will be tested using the same method as the primary endpoint at two-sided alpha 0.01. A participant with any bone marrow CR assessment between Days 22 and 42, inclusive, after start of induction or reinduction treatment will be considered an induction success; relapse and death events will be assessed following the last CR assessment during this time period. A participant with no CR assessments during this window will be considered an induction failure and imputed as such at randomization. Participants with induction success and no observed relapse or death events will be censored at the time they were last known to be alive. Maximum neutrophil and platelet counts within 7 days before or after the bone marrow draw will be used to determine count recovery. The key secondary analysis will be supplemented by a planned sensitivity analysis (not subject to alpha control), in which participants progressing to hematopoietic cell transplant will be censored at the time of transplant. The key secondary analysis will be conducted at the same time as the final primary OS analysis.

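### Table 7 defines failure for the secondary EFS endpoint by CRi alone, while Section 3 and the synopsis define the same endpoint by CR/CRi

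*Combined protocol and SAP*

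**What the plan says.** The protocol has two EFS endpoints: a key secondary one, in which failure to reach CR is an event, and a further secondary one. The failure rule bearing on the second appears in several places.

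- **Section 3, and the synopsis in the same terms:** "EFS following CR/CRI, with treatment failure defined as failure to achieve CR/CRI within 42 days of the start of induction", or of reinduction where that applies.
- **Section 8.2.2, Table 7, the endpoint's own row, labelled EFS following CRi:** "treatment failure is defined as failure to achieve CRi within 42 days of the start of induction/reinduction".
- **Section 8.2.2, Table 7, general induction-failure row:** "Failure to achieve CR (or CR/CRi) within 42 days of the start of induction therapy".
- **Appendix 7:** one generic treatment-failure entry, by CR only, and one generic EFS entry.

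Table 7 also defines the response categories. CR requires ANC above 1000/µL and platelets above 100,000/µL. CRi requires the other CR criteria, "absence of extramedullary disease), except for residual neutropenia" (at or below 1000/µL) or residual thrombocytopenia (at or below 100,000/µL). A note adds: "Participants with both residual neutropenia and residual thrombocytopenia are not considered to have achieved CRI".

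For the key secondary EFS, Section 9.4.2 says that a participant with no CR assessment in the Day 22 to 42 window "will be considered an induction failure and imputed as such at randomization". Section 9.4.3 applies the methods of the primary and key secondary analyses to the other time-to-event secondary endpoints.

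**The concern.** One endpoint has two different event definitions, and the one in the response table runs against the clinical ordering of the responses. Under it, a participant with full count recovery can be a failure while a participant with incomplete recovery is a success.

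The stake is the content of one secondary analysis. If the Table 7 wording were programmed, many of the best responders would enter as early events. A treatment that moved participants from CRi to CR would be penalized for doing so. That possibility is relevant here, because Section 2.2 links the drug's mechanism to platelet recovery and Section 9.4.3 tests platelet and neutrophil recovery formally. Leaving the conflict in place also leaves a choice between definitions to be made later, possibly with data in hand.

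**Working it through.** The plan gives no sample size, event count or power for this endpoint, so there is no figure to reproduce. The check is a comparison of definitions, followed by a count.

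**Step 1: do CR and CRi overlap?** (Table 7)

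| | ANC | Platelets |
|---|---|---|
| CR | above 1000/µL | above 100,000/µL |
| CRi, neutropenia only | at or below 1000/µL | above 100,000/µL |
| CRi, thrombocytopenia only | above 1000/µL | at or below 100,000/µL |
| Both low | not CRi, by the table's note | |

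No row of CRi is compatible with CR. At a given assessment the two are mutually exclusive.

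**Step 2: is CRi used elsewhere as shorthand for either response?** It is not. The combined response is written out where it is meant: in Section 3, in Table 7's general failure row, and in Section 6.1 ("Only participants with a documented response (CR or CRi) are eligible for consolidation").

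**Step 3: apply the two rules to a participant assessed only as CR.**

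- Section 3 rule (CR/CRi): success.
- Table 7 row (CRi): failure.

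**Step 4: count.** Inputs from Section 9.2 are N of about 570 and a planning CR rate of 50% in both groups. The CRi rate is not given, so 5% to 20% is assumed. One response category per participant is also assumed.

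- Failures under the Table 7 row = N × (1 − CRi rate)
- Failures under Section 3 = N × (1 − CR rate − CRi rate)
- Difference = N × CR rate = 570 × 0.50 = 285

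| Assumed CRi rate | Table 7 row | Section 3 | Difference |
|---|---|---|---|
| 5% | 541.5 (95%) | 256.5 (45%) | 285 |
| 10% | 513 (90%) | 228 (40%) | 285 |
| 15% | 484.5 (85%) | 199.5 (35%) | 285 |
| 20% | 456 (80%) | 171 (30%) | 285 |

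The difference does not depend on the assumed CRi rate. It does depend on no CR participant having had a qualifying CRi assessment earlier in the window. Anyone who did has achieved CRi and is not a failure, so 285 is an upper bound at a 50% CR rate.

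**Step 5: when would these events occur?** Section 9.4.2 places induction failures at randomization, but states this only for the key secondary EFS. Carrying it to this endpoint is an inference from the general sentence in Section 9.4.3.

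**The case against.** The strongest reply is that the intent is plain. Section 3 and the synopsis give both the name and the failure rule as CR/CRi. Within Table 7, the general failure row and the rows for relapse, cumulative incidence of relapse and relapse-free survival all allow for CR/CRi. The disputed row is nearly a copy of the row above it, and CRi alone is the outlier. No analyst would be likely to score complete remissions as failures. Section 9.4 also promises a more detailed SAP; no separate SAP text on this endpoint is available to check, and it may settle the matter.

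Most of this stands: it is very probably a drafting slip, not a deliberate analytic choice. It does not make the row harmless. The row limits its rule to this endpoint, so it reads as more specific than the general failure row. Section 3 sends the reader to Section 8.2.2 and Appendix 7 for definitions, and neither states the CR/CRi rule for this named endpoint. Section 9.4.2 gives an operational rule only for the CR version.

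Two further inferences are tempting but unsupported. One is that Table 7 overrides Section 3: nothing ranks them, and Section 3 states the failure rule itself. The other is that Appendix 7 supplies a third, rival definition: its failure entry is generic and fits the key secondary endpoint. It never names a CR/CRi-based EFS, so it is incomplete for this endpoint, not contradictory.

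**Conclusion.** The mismatch is real, and the Table 7 row is wrong as written. Taken literally, it would count up to about 285 of 570 participants as induction failures although they were in CR. That figure rests on the planning CR rate of 50% and on none of them having a prior CRi assessment in the window. Placing the events at randomization rests on reading Sections 9.4.2 and 9.4.3 together.

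A reader might infer that every complete remission becomes a failure, or that 285 misclassified participants are to be expected. Neither follows. A CRi that matures into CR within the window is not a failure under the rule, and the count arises only if the literal wording is implemented against Section 3 and the synopsis.

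The consequence is confined to one secondary analysis without multiplicity control. The fixed sequence in Section 9.4.3 covers MRD negativity, platelet recovery, neutrophil recovery and CR, and does not include this endpoint. OS and the key secondary EFS have their own consistent definitions. This is a minor but worthwhile correction.

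**What to change.** In Table 7, rename the row *EFS following CR/CRi* and define treatment failure for it as failure to achieve CR or CRi within 42 days of the start of induction/reinduction.

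As a consistency edit, extend the generic treatment-failure entry in Appendix 7 to *CR (or CR/CRi, for the corresponding endpoint)*, which matches Table 7's general failure row.

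The cost is two wording edits. They adopt the definition already in Section 3 and the synopsis and change no design element, sample size or error rate. They should be made before any unblinded analysis of this endpoint, so that the definition is not chosen afterwards.
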